12.4.4 Data management and statistical analysis software

1. Data management and statistical analysis software

Beijing Baiaozhi Information Technology Co., Ltd. clinical research integrated information platform (www.bioknow.net), using double independent input, check the correct statistical analysis. The statistical analysis adopts SAS9.13 software programming analysis.

(2) Setting of parameters in statistical analysis

The bilateral test (two-side test) was used for all hypothesis tests, and the α was 0.05. $P \leq 0.05$, the reliability of all confidence intervals was 95.

13. Test management

13.1 Programme compliance

The approved plan shall carry out the test, and any deviations from the plan shall be recorded.

13.2 Programme changes

13.2.1 Subject to the Ethics Committee's approval, this program shall be subject to developing a "program modification specification ", signed by the lead researcher. The proposal may be amended only with the consent of the applicant;

13.2.2 The program shall be amended and submitted to the Ethics Committee for approval before implementation;

13.2.3 Any person participating in the test shall follow the GCP principle and shall not violate the program. In the event of a breach of the program, it shall be recorded in the original record sheet.

13.3 Case report form (eCRF)

13.3.1 eCRF; completed by the researcher according to original records

13.3.2 Timely, accurate, complete, and reliable data recording;

13.3.3 The eCRF form shall be reviewed by the heads of the centers upon completion;

14. Test quality control

14.1 After the start-up of the project, the centers will hold in-hospital start-up meetings to train the pilot program, delirium assessment scale, and eCRF form;

14.2 Inclusion of cases in strict accordance with inclusion/exclusion criteria;

14.3 Both the applicant and the researcher shall implement a quality control and quality assurance system for clinical trials using standard operating procedures in the program:

- a) (a) The recording and preservation of raw materials must meet the GCP requirements;
- b) The laboratory must have inspection qualification to ensure that the inspection results are correct and reliable and can be properly preserved in the database;
- c) All observations and findings should be verified to ensure the reliability of the data. Ensure that the conclusions of clinical trials are derived from raw data and that quality control must be used at each stage of data processing;
- d) The applicant will monitor the research center on-site or by telephone during the middle and end of the study, when the sub-research center begins to be selected.
- e) The designated researcher shall be responsible for formulating and implementing the test rules;
- f) (b) Prior to the experiment, all the participants were trained in programs, operations, and GCP;
- g) Participants in the test should strictly abide by the provisions of the program, according to the procedures can not be arbitrarily changed;
- h) Designate statisticians to be responsible for the statistical processing of comprehensive data;
- i) The original records shall be kept by a particular person and kept in each sub-research center after the test.

15. Data preservation

According to the Clinical Trial Management Standard, the researcher should keep the clinical trial data until 5 years after the clinical trial.

16. Publication of papers

All research participants shall strictly keep confidential all information provided by the second Affiliated Hospital of Wenzhou Medical University, and at the same time require other participants and ethics committees to take the same confidentiality measures, without written permission, Information shall not be leaked to others.

The researcher and the applicant own all the data and results of this experiment. The researcher may not publish himself without the consent of the applicant. The applicant reserves the right to sign the paper. The applicant unit is the unit to which the project results belong.

2.1 Background and Rationale

Postoperative delirium is a common serious postoperative complication, especially in older people and is associated with increased mortality, morbidity, and healthcare costs^{2,3}. General anaesthesia and regional anaesthesia are routinely administered during surgery in elderly people. The choice and use of general anaesthesia and regional anaesthesia are predominantly based on the anaesthetist, discussion with the patients and their cares.

There is no clear consensus on which anaesthesia is associated with less incidence of postoperative delirium for older patients. The long-term objective is to assess whether regional anaesthesia results in a lower incidence of postoperative delirium than general anaesthesia among older patients undergoing hip fracture surgery.

2.2 Objectives

This clinical trial is pragmatic, multicentre, prospective, parallel grouped, randomised controlled. The RAGA trial aims to determine whether different types of anaesthesia (regional anaesthesia vs general anaesthesia) given to older patients undergoing hip fracture surgery result in the equivalent incidence of postoperative delirium.

This will be met through meeting the following aims (as specified in the protocol):

- Aim 1: To assess whether there are differences in the incidence of postoperative delirium in different groups (by age, existing cognitive impairment, or preoperative delirium) between groups;

- Aim 2: To compare the subtypes, severity, and duration of postoperative delirium between the anaesthesia groups;
- Aim3: To describe the pain scores in the postoperative period either regional anaesthesia or general anaesthesia;
- Aim4: To compare the occurrence of non-delirium complications between the groups;
- Aim 5: Assessment of the length of hospital stay between groups;
- Aim 6: Assessment of the mortality during the hospital stay and the follow-up period after hospital admission between groups;
- Aim 7: Assessment of the cognitive and functional decline and quality of life on 30 days, 6 months, and 12 months after surgery between groups.
- Aim 8: To assess the cost-effectiveness of using regional anaesthesia compared to general anaesthesia in terms of total in-hospital costs and expenditure of anaesthesia.

3. Study Methods

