- 1) Is there any difference between general anesthesia and local anesthesia in the occurrence, severity, attack type, and delirium duration after hip fracture in the elderly? Which anesthetic method can reduce the incidence of postoperative delirium?
- 2) Is there a difference in the effect of the two anesthetic methods on postoperative delirium in different older people (elderly, dementia, or delirium)?
- 3) Do various factors (hypotension, drugs, pain, etc.) during anesthesia affect postoperative delirium and extent?
- 4) To analyze whether the control of anesthesia can reduce the medical expenses and related economic benefits caused by delirium.
- 5) The relationship between the classification and duration of delirium and patients' prognosis; does delirium lead to long-term cognitive dysfunction? How does it affect patients and their families' quality of life? The survival rate in patients with delirium?

2. Research topics

A randomized, controlled, multicenter, prospective study of the effect of local and general anesthesia on postoperative delirium in elderly patients with hip fractures

3. Purpose of the study

To evaluate the effect of two anesthetic methods on the incidence and prognosis of delirium in elderly hip fracture

4. Research Design

using prospective, multicenter, large sample, randomized controlled study design. Randomly enter local anesthesia group or general anesthesia group at 1:1.

According to the domestic literature report of postoperative delirium in elderly patients, the sample size estimation estimated that postoperative delirium incidence is about 26. Assuming that postoperative delirium incidence after local anesthesia is less than 30% of general anesthesia, the calculated sample size is 441 $n\alpha=$ each group. The provisional total sample size is 1000 cases. The sample size can be adjusted according to the progress of the study and the results in the medium term.

The number of cases in each center is 100. Because of the central random system, the number of cases in each center can be automatically adjusted according to the actual situation of the subjects recruited.

5. Case selection

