3.3 Power and Sample Size

Based on the previously published incidence of postoperative delirium diagnosed using Confusion Assessment Method ranged from 28% to 50% in the elderly patients (age 65) during the hospital stay for hip fracture surgery, the observational studies in China estimated 3-day postoperative delirium incidences of 11.1%–23.3%.⁴⁻⁶ Assuming postoperative delirium incidences in general anaesthesia OF 26% and a reduction of 30% postoperative delirium in RA, 441 patients should be needed for each group to give power (1- β) of 80% and the significance level of 5% (two-sided). With an estimated drop-out rate of 10%, a total of 1000 patients will be recruited from the nine clinical trial centers in China.

4. Statistical Principles

Statistical analysis will be conducted in accordance with the plan outlined in the SAP. Statistical analysis will abide by these general statistical principles below.

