4.3 Multiple Comparisons

The primary outcome will be tested at 5% (two-sided) significance level. No corrections will be made for multiple comparisons, so intervals should not be used to infer treatment effects. As described in our research proposal, each comparison made will be hypothesis-driven and not hypothesis-generating.

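### SAP 2.2 states the overall aim as equivalent delirium incidence, but the trial is sized and tested for a difference and has no equivalence margin

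*SAP*

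**What the plan says.** SAP 2.2 gives the overall aim as determining whether regional and general anaesthesia "result in the equivalent incidence of postoperative delirium". Eight numbered aims follow. Aim 1 reads "To assess whether there are differences in the incidence of postoperative delirium in different groups", but the groups it means are defined by age, cognitive impairment or preoperative delirium, so it is a subgroup aim. None of the eight states the overall comparison of delirium incidence.

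The other relevant places concern a difference:

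- Protocol section 1, first research question: "Is there any difference between general anesthesia and local anesthesia in the occurrence", followed by which method can lower the incidence.
- SAP 2.1: "The long-term objective is to assess whether regional anaesthesia results in a lower incidence of postoperative delirium than general anaesthesia".
- SAP 3.3, from an incidence of 26% under general anaesthesia: "a reduction of 30% postoperative delirium in RA, 441 patients should be needed for each group", with 80% power at two-sided 5%.
- SAP 4.3: "The primary outcome will be tested at 5% (two-sided) significance level". SAP 8.1 tests the treatment term of a log-binomial model by chi-squared and reports a relative risk with its 95% confidence interval.
- Protocol 12.4.4: "The bilateral test (two-side test) was used for all hypothesis tests".

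Immediately after the primary-outcome sentence, SAP 4.3 adds: "No corrections will be made for multiple comparisons, so intervals should not be used to infer treatment effects".

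**The concern.** An equivalence aim and a difference aim need different evidence. To show equivalence, one fixes in advance the largest difference that would not matter and shows that the confidence interval lies inside it. A test of a difference can count against equal incidence when it is significant. When it is not significant, it shows only that a difference was not demonstrated.

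Under the wording of 2.2, a null result invites the reading that the two anaesthetics are equivalent. No passage says it will be read that way, but 8.1 contains no interpretation rule that would prevent it. The safeguard against that reading is the interval around the relative risk, which shows the effects still compatible with the data. Taken literally, SAP 4.3 tells the reader not to use that interval to infer a treatment effect, although 8.1 makes it the primary estimate.

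**Working it through.** **1. What the sample size was built for.** Inputs from SAP 3.3: p1 = 0.26; 30% relative reduction, so p2 = 0.26 × 0.70 = 0.182; difference 0.078; two-sided 5% (z = 1.96); 80% power (z = 0.8416).

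n per group = (1.96 + 0.8416)² × (0.26 × 0.74 + 0.182 × 0.818) / 0.078² = 440.3, rounded up to **441**.

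This is the SAP's figure. The pooled-variance form gives 444. The stated number is therefore a sample size for detecting a difference, and it is correct for that purpose.

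**2. Is there an equivalence rule?** Neither document contains a margin, two one-sided tests, or a comparison of the interval with a limit.

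**3. What a non-significant result leaves open.** The event counts below are hypothetical. General anaesthesia is fixed at 115/441 (26%). The p-value is from the uncorrected chi-squared test. The interval is exp(ln RR ± 1.96 × √[(1 − pR)/a + (1 − pG)/b]), where a and b are the event counts and pR and pG the proportions in the regional and general arms.

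| Regional events /441 | p | RR (95% CI) | CI includes 0.70? |
|---|---|---|---|
| 90 | 0.046 | 0.783 (0.614 to 0.997) | significant |
| 91 | 0.056 | 0.791 (0.622 to 1.007) | yes |
| 92 | 0.068 | 0.800 (0.629 to 1.017) | yes |
| 101 | 0.273 | 0.878 (0.696 to 1.108) | yes |
| 102 | 0.309 | 0.887 (0.704 to 1.118) | no |

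For regional counts of 91 to 101, the test is non-significant while the interval still includes the full 30% reduction. At 92 events the risk difference is −5.2 points (−10.8 to +0.4), which includes the planned 7.8 points.

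With 500 per arm and general anaesthesia at 130/500, the same holds for regional counts of 104 (p = 0.052, RR 0.800, 0.638 to 1.003) to 113 (p = 0.210, RR 0.869, 0.698 to 1.083).

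Identical observed counts (115 and 115 of 441) still leave a relative risk interval of 0.80 to 1.25. Whether that counts as equivalent depends on a margin the plan does not state.

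**4. How far the answer depends on the missing margin.** Assumptions: both true rates 26%, 450 evaluable per group (1000 less 10%, halved), and two one-sided tests at 5% each. The margins m are illustrations only and are not from the documents.

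SE = √(2 × 0.26 × 0.74 / 450) = 0.0292; power = 2Φ(m/SE − 1.645) − 1. For 80% power, n per group = 2 × 0.26 × 0.74 × (1.645 + 1.2816)² / m².

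| Assumed margin | Power at 450 per group | n per group for 80% power |
|---|---|---|
| 5 points | about 5% | 1319 |
| 7.8 points | about 69% | 542 |
| 10 points | about 92% | 330 |

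**The case against.** The strongest reply is that *equivalent* is a slip of language and not a competing design. The objective in 2.1 is directional, the sizing and the test are for a difference, 2.2 itself refers back to the protocol, and the English is rough elsewhere. No analyst would run a different primary analysis because of this word. This stands as a reading of intent and is why the point is minor. It does not remove the conflict: the 2.1 sentence is labelled a long-term objective within Background, and 2.2 is where the objectives are set.

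Second, the counts above are generic. Any difference trial with 80% power can give a null result whose interval includes its design effect, and rewording 2.2 would not change that. This is also true. The counts show why non-significance cannot answer the aim as written; they do not measure harm done by the word. The table also covers only one side: with 115 events under general anaesthesia, non-significance continues up to 141 regional events (p = 0.054).

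Third, the interval sentence in 4.3 sits under multiple comparisons, gives the absence of correction as its reason, and is probably meant for the secondary comparisons. Sections 4.1 and 8.1 will also put an interval beside the p-value. That is the natural reading, but the sentence directly follows the primary-outcome sentence and exempts nothing.

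Finally, not describing non-significance as equivalence is ordinary reporting practice, so the sentence suggested for 8.1 is a precaution. That is fair.

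**Conclusion.** The concern holds, at minor severity. The aim as worded in SAP 2.2 is one that the design, sized and tested for a difference and without a margin, cannot establish from a non-significant result. The sample size, endpoint, analysis set and test are not in error, and no analysis result would change. What is affected is the conclusion that may be drawn from a null primary result.

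On the SAP's own design figures and hypothetical counts, observed relative risks from 0.79 to 0.88 at 441 per arm (0.80 to 0.87 at 500) would be non-significant yet compatible with the full 30% reduction. The contradiction between passages rests on the text alone. The ranges rest on an observed general-anaesthesia incidence of 26% and equal arms with complete outcomes.

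**What to change.** Three sentences in the SAP:

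1. **Section 2.2.** Restate the overall aim as determining whether the 7-day incidence of postoperative delirium differs between regional and general anaesthesia, tested two-sided at 5%, with the trial sized to detect a 30% relative reduction under regional anaesthesia.
2. **Section 8.1.** Add that a non-significant primary result will be interpreted from the relative risk and its 95% confidence interval and will not be described as equivalence.
3. **Section 4.3.** Limit the caution about intervals to comparisons other than the primary outcome, so that it agrees with 8.1.

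The cost is editorial: sample size, endpoint, analysis set and test are unchanged. The sponsor gives up a claim of equivalence. If that claim is really wanted, a justified margin and a decision rule based on the interval must be written in before unblinding, and the sample size checked against that margin.

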3.1 Trial Design

This clinical trial is pragmatic, multicenter, prospective, parallel grouped, randomised controlled with cost-effective analysis. Participants will be randomised in a 1:1 ratio to regional anaesthesia or general anaesthesia.

3.2 Randomisation

Randomisation to regional anaesthesia or general anaesthesia is conducted in a 1:1 ratio, one day before surgery, using computer-generated assignment (web or telephone developed by the study data management provider).

3.3 Power and Sample Size

Based on the previously published incidence of postoperative delirium diagnosed using Confusion Assessment Method ranged from 28% to 50% in the elderly patients (age 65) during the hospital stay for hip fracture surgery, the observational studies in China estimated 3-day postoperative delirium incidences of 11.1%–23.3%.⁴⁻⁶ Assuming postoperative delirium incidences in general anaesthesia OF 26% and a reduction of 30% postoperative delirium in RA, 441 patients should be needed for each group to give power (1- β) of 80% and the significance level of 5% (two-sided). With an estimated drop-out rate of 10%, a total of 1000 patients will be recruited from the nine clinical trial centers in China.

4. Statistical Principles

Statistical analysis will be conducted in accordance with the plan outlined in the SAP. Statistical analysis will abide by these general statistical principles below.

4.1 Confidence Intervals and p-values

All estimates of differences between groups would be presented with two-sided 95% confidence intervals unless otherwise stated. Statistical significance will be considered if $p < 0.05$ (two-sided).

4.2 Modeling Principles

Intervention groups will be compared using a log-binomial regression model.

4.3 Multiple Comparisons

The primary outcome will be tested at 5% (two-sided) significance level. No corrections will be made for multiple comparisons, so intervals should not be used to infer treatment effects. As described in our research proposal, each comparison made will be hypothesis-driven and not hypothesis-generating.

4.4 Analysis Sets

4.4.1 Enrolled

The Enrolled set will include all patients who have provided informed consent and have been included in the study database.

4.4.2 Full Analysis Set

The Full Analysis Set (FAS) will be defined as all patients randomly assigned to a treatment group having at least one efficacy assessment after randomisation.

4.4.3 Per Protocol Analysis Set

The Per Protocol Analysis Set (PPS) will include all randomised patients meeting the study eligibility criteria, at least one efficacy assessment after randomization. Patients who have one or more protocol deviations would be excluded.

4.5 Missing Data

In the primary outcome analysis, postoperative delirium, the missing values in Full Analysis Set will not be imputed.

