12.4.1 Analysis of data sets

(1) Total Analysis Set (FAS): A collection of all cases randomly enrolled and treated with at least one trial drug.

When analyzing the main curative effect index, the FAS concentration's missing value is processed by carrying the results observed at the last time point to the current (LOCF) method.

An Available Case Analysis principle is used to deal with the missing value in the analysis of secondary efficacy index, general condition, and safety.

(2) Conformity with program set (PPS): a collection of cases that meet the inclusion criteria and complete treatment in accordance with the provisions of the trial program, i.e., cases that meet the trial program, have good compliance, have not taken banned drugs, and have completed the evaluation of effectiveness (at least primary efficacy), if any.

(3) Security data set (SAS): at least one treatment and actual data recorded with a safety indicator evaluation.

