4.6 Analysis Populations

All analyses of primary and secondary outcomes, including safety outcomes, will be based on intention-to-treat. Participants would be analysed in the intervention group to which were randomised, and all participants shall be included whether or not they received the allocated intervention.

As a sensitivity analysis, a per-protocol analysis would also be carried out for the primary outcome and secondary outcomes.

5. Definition and Derived variables

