5.1 Primary outcome

The primary outcome is the incidence of an episode of delirium during the first 7 postoperative days, assessed daily by the Confusion Assessment Method. An episode is defined if both acute onset and fluctuating course and inattention criteria were met, and one or both of either disorganised thinking or altered levels of consciousness criteria were met.

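### The per-protocol set has no time limit on exclusions and the status of sedatives given after delirium is undefined, so patients could leave the SAP's only named sensitivity analysis because they had the primary outcome

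*SAP*

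**What the plan says.** **Per-protocol set.** SAP 4.4.3 takes randomised, eligible patients with at least one efficacy assessment and excludes anyone with a protocol deviation. It gives no list, grade or time limit. The protocol's version (12.4.1) requires good compliance and no banned drugs, also without a time limit. SAP 4.6 gives the set its role: "As a sensitivity analysis, a per-protocol analysis would also be carried out for the primary outcome and secondary outcomes". Protocol 12.4.2 has both per-protocol and intention-to-treat analyses of the main efficacy indicators.

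**Sedatives.** Protocol section 7, item 1, restricts sedatives before, during and after surgery and asks that postoperative use be recorded in detail. Item 5, on postoperative analgesia, tells both groups to avoid them. Section 1 says that diazepam or psychotropic drugs are often required after delirium. The description under section 9 leaves further diagnosis and treatment of delirium to be decided with the responsible physician.

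**Missing primary data.** Protocol 12.4.1 defines its full analysis set as "A collection of all cases randomly enrolled and treated with at least one trial drug", in which a "missing value is processed by carrying the results observed at the last time point to the current (LOCF) method". SAP 4.5 says: "In the primary outcome analysis, postoperative delirium, the missing values in Full Analysis Set will not be imputed". The SAP's full analysis set is "all patients randomly assigned to a treatment group having at least one efficacy assessment after randomisation", while SAP 4.6 says "all participants shall be included whether or not they received the allocated intervention". SAP section 4 states: "Statistical analysis will be conducted in accordance with the plan outlined in the SAP". The endpoint in SAP 5.1 is the "incidence of an episode of delirium during the first 7 postoperative days, assessed daily by the Confusion Assessment Method". Protocol section 10 adds medical and nursing records as a source for delirium status.

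**The concern.** A per-protocol analysis is useful as a check only if membership of the set does not depend on the outcome. Here a path from outcome to exclusion is open: delirium occurs, a sedative or similar drug is given, the use is classed as a deviation or banned drug, and the patient leaves the set. The patients lost would then be cases of the primary outcome. Observed risks would fall in both arms, and the relative risk would shift if the share removed differed by arm. Agreement or disagreement with the intention-to-treat result would then be hard to interpret.

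The lesser worry is the primary endpoint in patients whose CAM assessments are all negative but incomplete. The SAP does not say whether they are non-cases or missing, and a rule chosen after the data are seen leaves room for choice.

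**Working it through.** **Design figures (SAP 3.3).** GA risk 0.26; RA risk 0.26 × 0.70 = 0.182; 80% power; two-sided 5%. The unpooled formula gives n = (1.960 + 0.842)² × (0.26 × 0.74 + 0.182 × 0.818) / 0.078² = 440.3, so 441 per group, as the plan states. Allowing 10% drop-out, 441 / 0.9 = 490 per group, 980 in total; the plan takes 1000. The sample size is not in question.

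Everything below uses expected counts with 500 per arm and a chi-square test without continuity correction. Complete data: 91 versus 130 events, RR 0.70, p = 0.003.

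**Per-protocol removal.** Let x be the share of delirious patients removed (assumed; the documents give none). The remaining risk is p(1 − x) / (1 − px).

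| True RR | x in RA | x in GA | RA | GA | RR | p |
|---|---|---|---|---|---|---|
| 0.70 | 0.30 | 0.30 | 63.7/472.7 | 91.0/461.0 | 0.68 | 0.010 |
| 0.70 | 0.30 | 0.20 | 63.7/472.7 | 104.0/474.0 | 0.61 | 0.0006 |
| 0.70 | 0.20 | 0.30 | 72.8/481.8 | 91.0/461.0 | 0.77 | 0.061 |
| 1.00 | 0.30 | 0.20 | 91.0/461.0 | 104.0/474.0 | 0.90 | 0.41 |
| 1.00 | 0.20 | 0.30 | 104.0/474.0 | 91.0/461.0 | 1.11 | 0.41 |

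Harsher assumptions give larger shifts. Suppose 5% of delirium-free patients are also removed, so that the risk is p(1 − x) / [p(1 − x) + 0.95(1 − p)]. With x = 0.50 in RA and 0.30 in GA, RR = 0.105 / 0.206 = 0.51. The reverse gives 0.141 / 0.156 = 0.90. The size is set by the assumption.

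**Incomplete negative records.** Assume 100 of 1000 patients are incomplete, i in a given arm, and that a share c of their delirium (50–75%) is still captured. Events = (500 − i)p + ipc. The denominator is 500 if incomplete negatives are scored as non-cases, or (500 − i) + ipc if they are dropped.

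| Incomplete GA/RA | RR, non-case | RR, dropped |
|---|---|---|
| 50/50 | 0.70 | 0.70 |
| 40/60 | 0.69 | 0.72 |
| 60/40 | 0.71–0.72 | 0.69 |
| 25/75 | 0.66–0.68 | 0.74–0.75 |
| 75/25 | 0.72–0.74 | 0.66–0.67 |

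The largest p in this table is 0.018 (25/75, dropped, c = 0.75).

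A wider imbalance shows why the rule should be written down. Suppose all delirium is captured, but 10% of delirium-free GA patients and 30% of delirium-free RA patients are incomplete. Scoring them as non-cases leaves RR at 0.70. Dropping them gives (91/377.3) / (130/463) = 0.86, and the reverse split gives (91/459.1) / (130/389) = 0.59.

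**Tipping point (50/50, c = 0.5, scored as non-cases).** Captured events are 86.45 in RA and 123.5 in GA. Credit GA with its expected 6.5 missed cases among 43.5 incomplete negatives (15%). RA then needs 18 of 45.45 (40%) before p passes 0.05: (86.45 + 18) / 130 = 0.803, p = 0.057. With 17, p = 0.047.

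**The case against.** The strongest reply is that the per-protocol path is inferred. The sentence linking delirium to diazepam is background, not a treatment rule. Item 5 of section 7 concerns analgesia. Item 1 asks for sedative use to be recorded and does not call it a deviation. Treatment of delirium is left to clinical decision, so it may be within protocol. All of this stands: the documents leave the status of such drugs undefined, and the claim is conditional on it. It does not remove the point, because SAP 4.4.3 excludes for any deviation at any time and leaves that status to whoever builds the set.

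It is also fair that no passage gives a reason for removal to differ by arm, that equal removal barely moves the RR, and that the null examples (p = 0.41) would not produce a false claim.

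On missing data, a reader might infer that the two documents leave the primary analysis unsettled. They do not. SAP section 4 makes the SAP govern, so the carry-forward conflict is mostly housekeeping. One positive CAM settles the endpoint, medical and nursing records also count under the protocol, and the natural reading of the SAP is that other assessed patients are non-cases. That reading is simply not written. The mismatch between the full analysis set and the intention-to-treat statement changes no estimate by itself: without imputation, a patient with no assessment cannot enter the model.

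**Conclusion.** The point holds for the per-protocol set, conditionally: if drugs given for delirium count as deviations or banned drugs, patients leave the set because they had the primary outcome. The passages on sedatives, delirium treatment and deviations must be reconciled. With assumed removal of 20–30% of delirious patients, a true RR of 0.70 appears as 0.61 to 0.77, and a true RR of 1.00 as 0.90 to 1.11. With equal removal of 30% the shift is only to 0.68.

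A reader might go further and infer that the trial's main result is biased. The documents do not support that. The intention-to-treat analysis is untouched by the per-protocol rule, and nothing shows that such removals occurred or differed by arm. The incomplete-record question is minor: with balanced incompleteness both readings give 0.70, and they separate only under an assumed imbalance between arms. Overall this is a cheap improvement to a supporting analysis, not a threat to the primary one.

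**What to change.** **Main change.** In SAP 4.4.3, base per-protocol exclusions only on eligibility violations and on deviations up to the end of surgery, and say that this replaces the protocol's definition. Drugs given after surgery then cannot remove a patient. A fixed time point also works for patients with preoperative delirium, who are eligible and form a planned subgroup. This concerns the analysis set only, not whether such drugs may be given. The sponsor should separately reconcile the sedative passages; if that amends the protocol, section 13.2 requires ethics approval first.

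**Same SAP edit, minor.** In 4.5 and 5.1, state that the protocol's carry-forward rule is superseded, that any positive CAM or record-confirmed episode is a case, and that incomplete negative records are non-cases in the primary analysis. Report incomplete records by arm and add one tipping-point sensitivity analysis.

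**Cost.** Wording and a little programming, with no new patients or visits. The per-protocol set becomes slightly less pure. Scoring incomplete negatives as non-cases can undercount delirium; the tipping-point analysis shows how much that could matter.
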